## **Introduction:**

COVID-19 is an infectious viral disease caused by SARS CoV-2 (severe acute respiratory syndrome-corona virus 2) that has affected large number of people all over the world with high mortality rate (1). COVID-19 infection has been classified(2) as

1- Mild Illness: Individuals who have any of the various signs and symptoms of COVID-19 (e.g., fever, cough, sore throat, malaise, headache, muscle pain, nausea, vomiting, diarrhea, loss of taste and smell) but who do not have shortness of breath, dyspnea, or abnormal chest imaging.

2-Moderate Illness: Individuals who show evidence of lower respiratory disease during clinical assessment or imaging and who have an oxygen saturation ( $\text{SpO}_2$ )  $\geq 94\%$  on room air at sea level.

3-Severe Illness: Individuals who have  $\text{SpO}_2 < 94\%$  on room air at sea level, a ratio of arterial partial pressure of oxygen to fraction of inspired oxygen ( $\text{PaO}_2/\text{FiO}_2 < 300$  mm Hg, respiratory frequency  $> 30$  breaths/min, or lung infiltrates  $> 50\%$ ).

4-Critical Illness: Individuals who have respiratory failure, septic shock, and/or multiple organ dysfunctions.

Covid-19 pandemic stimulates research works to find a solution to this crisis from starting 2020 year up to now. With ending of 2021 year, various advances in pharmacotherapy against COVID-19 have emerged (3).

Regarding antiviral drugs used in treatment of COVID-19, remdesivir has approved by Food and drug administration (FDA)(4). Other drugs have shown controversial antiviral activity include: favipravir, ivermectin, nitazoxanide, hydroxychloroquine, ribavirin (5).

Recently, with the end of 2020, immunotherapy to target virus antigen has developed (6).Figure 1 shows two types of immunotherapy include active and passive immunotherapy. Active immunotherapy is to enhance body to produce antibodies against virus as by vaccination. Passive immunotherapy involves direct administration of prepared antibodies acting specifically against virus or administration of product containing antibodies like plasma (6).

In this study, the point of research is antibodies cocktail including REGN3048-3051(**casirivimab and imdevimab**). There are three targets for these antibodies to work as antiviral including:

- 1) antibodies that prevent the virus attachment and entry
  - 2) antibodies that inhibit the virus replication and transcription
  - 3) antibodies that hinder various steps of the immune system response
- Table 1 includes various types of antibodies under investigation for treatment of COVID-19 and their targets(6).

REGN3048 and REGN3051 are human monoclonal antibodies (mAb) targeting the spike glycoprotein on surface of viral particles thereby preventing viral entry into human cells through the angiotensin-converting 2(ACE2) enzyme receptor (7, 8), and have shown promising antiviral activity and need for further investigation to prove their benefit in COVID patients(9).

Previous study(9) on REGN3048-3051 has mentioned that both efficacy and safety of this antibodies cocktail are proved in COVID-19 outpatients treatment in both low (2.4 g of REGN-COV2), or high (8.0 g of REGN-COV2) dose when compared to placebo, Efficacy is measured as

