## **Aim of the study:**

1-To evaluate the efficacy of antibodies cocktail (casirivimab and imdevimab) compared to standard antiviral therapy in reducing 28-day mortality in hospitalized patients with moderate, severe or critical COVID19

2-To evaluate safety of antibodies cocktail (casirivimab and imdevimab) compared to standard antiviral therapy by monitoring of hypersensitivity and infusion related reactions or other significant adverse effects

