### **Exclusion criteria**

Patient should not have any of the following to be included:

1-history of hypersensitivity or infusion related reactions after administration of monoclonal antibodies.

2-prior use of standard antiviral therapy (remedsvir or favipravir).

3-Current use of controversial antiviral therapy (hydroxychloroquine, ivermectin, nitazoxanide, oseltemavir, acyclovir, ribavirine, lopinavir/rotavirus, sofosbuvir, dectasevir, semipiravir, azithromycin).

4-patients expected to die within 48 hours.

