## **Interventions:**

Population included in this study will be assigned into 3 groups with 1:2:2 ratios to receive either antibodies cocktail or standard antiviral therapy (remdesvir, favipravir) as shown in table2 and figures 2 & 3.

Group A patients will receive REGN3048-3051(Antibodies cocktail (casirivimab and imdevimab) ) in low-dose regimen 1.2 gm (1200 mg of combined antibodies) diluted in 250 ml 0.9% sodium chloride solution as single I.V infusion over 30-60 minutes.

Group B patients will receive Remdesivir :

Day1 (loading dose): 200 mg (two 100mg vials) diluted in 500ml 0.9% sodium chloride solution infused I.V over 60 minutes

Day 2-5 or Day 2-10 (maintenance dose): 100 mg (one 100mg vial) in 250 ml 0.9% sodium chloride solution infused I.V over 30 minutes

Group C patients will receive Favipravir :

[figure not shown]
Day 1 (loading dose): 1600 mg (8 tablets) or 1800 mg (9 tablets) orally or in Ryle tube / 12 hours

Day 2-5 or day 2-10 (maintenance dose): 600 mg (3 tablets) or 800 mg (4 tablets) orally or in Ryle tube / 12 hours

[figure not shown]
Patients will be received standard of care by Physicians, Clinical pharmacist , Nurses and as guided by Egyptian COVID-19 treatment protocol.

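### Aim 1 compares the cocktail with a class that mixes remdesivir and favipiravir, favipiravir is described inconsistently, and no cocktail contrast is named, so a significant mortality test could come from favipiravir alone

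*Combined protocol and SAP*

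**What the plan says.** The Introduction describes two kinds of antiviral drug. Of one it says "remdesivir has approved by Food and drug administration (FDA)(4". Of the rest it says "Other drugs have shown controversial antiviral activity include: favipravir, ivermectin, nitazoxanide, hydroxychloroquine, ribavirin".

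Later sections group the drugs differently. Exclusion criterion 2 bars "prior use of standard antiviral therapy (remedsvir or favipravir", and the Interventions section says that patients will "receive either antibodies cocktail or standard antiviral therapy (remdesvir, favipravir". Exclusion criterion 3 uses the word controversial again, for "Current use of controversial antiviral therapy (hydroxychloroquine, ivermectin, nitazoxanide, oseltemavir, acyclovir, ribavirine" and others. That list contains the other four drugs from the Introduction's sentence but not favipiravir.

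Aim 1 in Aim of the study is efficacy "compared to standard antiviral therapy in reducing 28-day mortality in hospitalized patients", with the comparator given as a single class. The Statistical Analysis Plan compares 28-day mortality across the groups by Kruskal-Wallis with a P-value. It names no pairwise contrast and has no rule for or against combining the two comparator groups. Table 2 and Sample Size give 53 patients on cocktail (A), 106 on remdesivir (B) and 106 on favipiravir (C).

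**The concern.** Aim 1 asks about the cocktail, but the only planned mortality test asks whether any of three groups differs from any other. A test of that kind can reject because the two comparators differ from each other while the cocktail matches one of them. The protocol itself describes the evidence for the two comparators in different terms, so a difference between them is a possibility that its authors had reason to consider.

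What is at stake is the wording of the main conclusion. After a significant test, nothing in the plan says which comparison answers aim 1. A report could say that the cocktail did better than standard antiviral therapy when all the evidence came from the favipiravir arm and nothing had been shown against remdesivir. Naming a single cocktail contrast would not prevent this if that contrast combined B and C.

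**Working it through.** **1. The plan's own figure.** Sample Size gives 246 for 80% power, an effect of 0.2 and alpha 0.05. One-way ANOVA with three equal groups and Cohen's f = 0.2 reproduces it exactly (N = 246, power 0.804). The trial is therefore sized for a three-group test, not for a cocktail contrast.

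**2. Where favipiravir is placed.**
- Introduction: among drugs of controversial activity, apart from remdesivir.
- Exclusion criterion 2: standard, with remdesivir.
- Exclusion criterion 3: missing from the controversial list, which has the Introduction's other four drugs.
- Interventions: standard, with remdesivir.

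Favipiravir's share of the comparator class is 106/(106 + 106) = 50%.

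**3. Inputs for the illustration.** The group sizes are those of Table 2. (Population states the ratio as 2:1:1, which does not match them.) The mortality rates are assumed: A 38%, B 38%, C 58%. They lie around the 48% implied by Sample Size, 120 deaths/250 admissions per month, if the current admission rate also held in the months when the deaths were counted.

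**4. Three-group test.** For a yes/no outcome, Kruskal-Wallis is the Pearson chi-square times (N − 1)/N, here 264/265.
- Overall rate: (53×0.38 + 106×0.38 + 106×0.58)/265 = 121.9/265 = 0.46.
- Noncentrality: (53×0.08² + 106×0.08² + 106×0.12²)/(0.46×0.54) = 2.544/0.2484 = 10.24.
- Probability that a chi-square on 2 df with this noncentrality exceeds 5.99: 0.825. Simulation gives 0.83.

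A and B are identical here, so the rejections are driven by C.

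**5. Pooled comparison, if someone made one.** The pooled comparator rate is (38 + 58)/2 = 48%, a difference of 10 points from A.
- Null standard error: √[0.46×0.54×(1/53 + 1/212)] = 0.0765.
- Alternative standard error: √[0.38×0.62/53 + 0.48×0.52/212] = 0.0750.
- Φ[(0.10 − 1.96×0.0765)/0.0750] = Φ(−0.67) = 0.25. Simulation gives about 26% of trials significant in favour of A.

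**6. A versus B directly.** The true difference is zero. Simulation gives significance in favour of A in about 2.4% of trials, which is the nominal one-tail error.

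**7. Other assumed rates.**

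| A/B/C | Three-group test | Pooled, favours A | A vs B, favours A |
|---|---|---|---|
| 28/28/48% | about 85% | 26–27% | about 2.3% |
| 38/38/58% | about 83% | about 26% | about 2.4% |
| 48/48/68% | about 83% | about 26% | about 2.3% |

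**8. Power of the alternatives, 28% on A versus 48% on B and C.**
- 53 vs 106: overall rate 65.72/159 = 0.413; standard errors 0.0828 and 0.0785; Φ[(0.20 − 1.96×0.0828)/0.0785] = 0.68.
- The same contrast at two-sided 0.025 (the first Holm step with two contrasts, z = 2.241): Φ[(0.20 − 2.241×0.0828)/0.0785] = 0.57.
- 53 vs 212 pooled: overall rate 0.44; standard errors 0.0762 and 0.0706; Φ[(0.20 − 1.96×0.0762)/0.0706] = 0.76.
- Planned three-group test: noncentrality (53×0.16² + 212×0.04²)/(0.44×0.56) = 1.696/0.2464 = 6.88; power 0.65 (0.67 by simulation).

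**The case against.** The best defence is that strength of evidence and routine use are different things. A drug can be standard locally while its evidence is disputed. The Introduction never defines standard, and where the protocol says which drugs it means by that term, it includes favipiravir. Sample Size justifies the allocation ratio by how many patients actually get each drug, and Interventions refers to the Egyptian treatment protocol. Both hint that standard means local practice. This stands in part. A reader might infer that, by the protocol's own classification, half of the comparator is not standard. The documents do not support that inference, because they set no criterion for the word. Equally, they never state the local-use meaning.

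The exclusion lists add little. Criterion 3 has 11 entries, only four of them from the Introduction's sentence, and a trial drug could hardly be barred there. The label changes no eligibility decision. This stands.

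The pooled comparison is not planned. The arms are separate throughout, and the word superiority does not appear. A reader might infer that the plan will pool B and C, or that the 83% is the chance of a false claim against standard therapy. Neither follows. The plan is silent on pooling, and the 83% is the chance that the three-group test detects C's higher mortality. With separate arms, a careful reader could see which drug drove the result.

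Finally, the missing contrast would matter even if both comparators were beyond dispute. That is true, and it is why the remedy lies mainly in the SAP and only secondarily in the labels.

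**Conclusion.** The concern holds in limited form. Favipiravir is described in two ways without reconciliation, aim 1 uses the mixed class as its comparator, and the only planned mortality test cannot say whether the cocktail differs from either drug. When the cocktail equals remdesivir and favipiravir is 20 points worse, that test is significant in about 83% to 85% of trials. A pooled comparison, if made, would favour the cocktail in about 26% to 27%, against about 2.3% to 2.4% for a direct comparison with remdesivir.

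These figures rest on assumed mortality rates, on a 20-point gap between the comparators for which the documents give no basis, on full follow-up at 53/106/106, and on groups comparable at baseline. They show what the plan permits and do not forecast the result. Whether favipiravir deserves to be called standard cannot be settled from the documents, and the point does not depend on it.

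**What to change.** - In Aim of the study and the Statistical Analysis Plan, name two 28-day mortality contrasts, cocktail versus remdesivir and cocktail versus favipiravir, each with its estimate and confidence interval. Control multiplicity across the two, for example by Holm.
- State that the remdesivir and favipiravir groups will not be pooled for the aim 1 conclusion, and that the conclusion will name the drug or drugs against which a difference was shown.
- Reconcile the description of favipiravir in the Introduction, Exclusion criteria and Interventions. One sentence saying whether standard means local use would do. Reserving the word for remdesivir is not required.

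The change is to wording only; no arm or sample size is altered. The cost is power: about 68% per contrast for 28% versus 48% before adjustment, and about 57% at the first Holm step, against about 76% for a pooled 53 versus 212. The pooled contrast is not in the plan, however. The planned three-group test itself has about 65% to 67% power in that scenario, so the real loss comes from the multiplicity adjustment.

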#### 1-Virologic Efficacy

Time-weighted average change from baseline in viral load through day 7 (log10 scale) in patient.

#### 2-Clinical Efficacy

Percentage of patients with one or more medically attended visits

- Symptoms offset at day 7

Safety is measured as

Percentage of treated patients who experience infusion related and hypersensitivity reactions and incidence of any serious and unexpected adverse effect.

This previous study(9) concluded that efficacy is greater and more obvious in seronegative outpatients (whose immune response is not developed yet to produce antibodies against virus) and with high baseline viral load outpatients.

Now, data(10) is available for these new antibodies cocktails. The U.S. Food and Drug Administration (FDA) has allowed an Emergency Use Authorization (EUA) for casirivimab and imdevimab combination in the treatment and post-exposure prophylaxis of mild to moderate COVID-19 in adults and pediatric outpatients (more than 12 years of age and not less than 40 kg) with positive Polymerase Chain Reaction (PCR) results of direct SARS-CoV-2 viral testing, and who are at high risk for progression to severe COVID-19 requiring hospitalization or causing death.

In contrast, REGN3048 and REGN3051 are still not authorized for use in patients(10):

- who are hospitalized due to COVID-19, OR
- who require oxygen therapy due to COVID-19, OR
- who require an increase in baseline oxygen flow rate due to COVID-19 in those on chronic oxygen therapy due to underlying non-COVID-19 related comorbidity(10).

Now, casirivimab and imdevimab are approved investigational antibodies, Serious and unexpected adverse effects can occur that not previously reported with their use(10).

Confirmed adverse effects include hypersensitivity and infusion related reactions and the study have showed that there is no difference in safety profile between intravenous (I.V) infusion and subcutaneous (S.C) injection. Data about use during pregnancy and breastfeeding mother is insufficient yet. Also, Data not support any dosage adjustment in hepatic and renal patients (10).

This antibody combination follows linear pharmacokinetics after its single intravenous doses with half-life of about 25 to 37 days for both antibodies. Regarding elimination, this combination is not metabolized by liver cytochrome enzymes ,and not excreted by kidneys (10).

Limitations of previous study include

1-short duration of follow up

2-not used much clinical relevant outcomes like mortality rate

3- Not studied the long term effect of antiviral efficacy in lowering viral load on inflammatory markers.

4- Study performed on non-hospitalized patients and not included hospitalized patients (trial is done only on outpatients and not inpatients)

[figure not shown]

Fig.1: Immunization approaches against COVID-19(6)

Table 1 shows antibodies candidate against SARS-CoV-2 under investigation by pharmaceutical companies(6).

Antibody	Mechanism	Company	Stage of study/identification method
VIR-7831/VIR-7832	
 
-Neutralize highly conserved epitope in s protein
 
-Induce NK-mediated antibody-dependent cell cytotoxicity
 
	VIR biotechnology and GSK	Designed based on S309 (isolated from SARS-CoV patients)
SAB	Anti SARS-CoV-2 fully human poly clonal antibodies	SAB Biotherapeutics	
 
-Antibodies produced in genetically engineered cattle
 
will enter clinical trial by early summer
 
-SAB-301 against MERS passes phase 1 of clinical trial and entered phase II/III
 

-	Target multiple viral S epitope	ImmunoPrecise	Using B cell Select® and Deep Display® technology
COVID-HIG and COVID-	Hyperimmune polyclonal antibody derived from	Emergent BioSolutions	Enter clinical trial within 4–5 months

EIG	human plasma or immunized horse		
Rcig	Recombinant anti SARS-CoV-2 hyperimmune gammaglobulin, polyclonal antibodies	GigaGen	
 
-Preclinical stage
 
-Aimed for COVID19 hospitalized patients and prophylaxis in high risk individuals
 

Antibody cocktail including REGN3048-3051	Fully human multivalent antibodies against the spike protein isolated from genetically modified mice or recovered COVID-19 patients	Regeneron	
 
-Phase 1 clinical trial for Middle East Respiratory Syndrome (MERS) completed last year
 
-Clinical trial for SARS-CoV-2 starts by early summer
 

## **Aim of the study:**

1-To evaluate the efficacy of antibodies cocktail (casirivimab and imdevimab) compared to standard antiviral therapy in reducing 28-day mortality in hospitalized patients with moderate, severe or critical COVID19

2-To evaluate safety of antibodies cocktail (casirivimab and imdevimab) compared to standard antiviral therapy by monitoring of hypersensitivity and infusion related reactions or other significant adverse effects

## **Population:**

265 COVID-19 PCR confirmed patients with indication for antiviral therapy is included in this study and will be randomized (2:1:1) into 3 groups

1- Group A: REGN3048-3051(Antibodies cocktail (casirivimab and imdevimab) )

2-group B: Remdesivir

3-group C: Favipravir

Population in this study are patients hospitalized in isolation hospital- Mansoura university.

A computer file containing a written informed consent from included patients will be provided. Paper will not be a tool for providing agreement by patients or their relatives to avoid transmission of infection.

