**Figure 2: Assignment of the included COVID cases at their groups.**

**Figure 3: Frequency of interventions in included patients**

## **Method:**

The type of this study is single blind non-RCT and is considered a Phase IV Clinical trial (post-marketing study) to report efficacy and safety of new medicine.

We use PubMed search tool to find clinical studies that performed to test efficacy and safety of developed immunotherapy in treatment of COVID-19 with about 4,000 results with focusing on antibodies developed as antiviral against COVID-19 obtaining only 70 results from which REGN-COV2, a Neutralizing Antibody Cocktail is selected with its only one clinical study up to now (REGN-COV2, a Neutralizing Antibody Cocktail, in Outpatients with Covid-19) which is published in New England Journal of Medicine on January 21, 2021.

Another resource used to obtain data is Fact Sheet for Health Care Providers-EUA OF casirivimab and imdevimab which provides clinical data about the use of this antibodies cocktail. Endnote citation software is used for citation of references.

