## **Statistical Analysis Plan (SAP):**

Intention-to-treat strategy will be used in this study. Intention-to-treat strategy will be used in this study. Statistical analysis will be achieved with SPSS, version 26.

Categorical variables will be presented as proportion and percent. Continuous variables will be presented as mean (standard deviation) for parametric data or as a median (25th-75th percentile) for non-parametric data.

Regarding baseline characteristics, Kruskal-Wallis or ANOVA test (depending on type of data and the continuous data distribution (normal or not)) will be used to compare these characteristics between the study groups. We will report the P-value for our statistical tests with level of statistical significance will be P-value  $\leq 0.05$ .

In case of existing differences in some baseline characteristics, logistic regression will be performed. This allows studying the effect of these variables on the primary outcomes of the study to exclude the effect of these confounding variables and to ensure the effect on the outcomes is due to interventions.

Regarding the outcomes, we will compare the 28-day all-cause mortality rate, result of PCR test at hospital discharge and incidence of infusion related or hypersensitivity reactions during and after the end of drug infusion (primary outcome) using the Kruskal-Wallis test with reporting the P-value.

While the secondary outcomes (hospital stay duration, icu stay duration and others) are compared using Kruskal-Wallis or ANOVA test depending on type of data and the distribution of data (normal or not)

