## **Sample Size:**

A total sample sizes of 246 patients would achieve at least 80 % power to detect a risk difference of 0.2 (20%) in the 28-day all-cause mortality (primary outcome) with a significance level ( $\alpha$ ) of 0.05 and 95% confidence level using the ANOVA or Kruskal-Wallis test of independent proportion in G\*Power software. To compensate for the estimated loss-to-follow-up and increase the study power, we will increase the sample size in both remdesivir and favipravir groups to be 106 patients compared to 53 patients in Antibodies cocktail Group As Antibodies cocktail product is available for only about 50 COVID-19 patients. In addition, the ratio (1:2:2) is the closest to reality according to number of patients who receive each drug.

The mortality data was estimated from the average mortality in August, September, and October 2021 at the Mansoura University Isolation Hospital among all hospitalized patients. Mortality rate is found to be about 360 cases in these 3 months (120 cases / month). The online system has been used to obtain mortality rate in these three months.

The current admission rate at the Mansoura University – Isolation Hospital is 250 cases per month on average; our needed sample is about 250 cases.

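### The study is called both randomised (2:1:1) and a non-RCT, while its group sizes follow 1:2:2; the primary analysis depends on an assignment method that the readable text never states

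*Combined protocol and SAP*

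**What the plan says.** All references are to the combined protocol and SAP.

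- **Population:** the 265-patient sample "is included in this study and will be randomized (2:1:1) into 3 groups". The groups are listed as A (antibody cocktail), B (remdesivir) and C (favipiravir).
- **Interventions:** patients are "assigned into 3 groups with 1:2:2 ratios". Table 2 gives A 53, B 106 and C 106.
- **Method:** "The type of this study is single blind non-RCT".
- **Sample Size:** the two comparator groups are enlarged "to be 106 patients compared to 53 patients in Antibodies cocktail Group", because the "Antibodies cocktail product is available for only about 50 COVID-19 patients". It adds that "the ratio (1:2:2) is the closest to reality according to number of patients who receive each drug".
- **Figure 2:** its caption reads "Assignment of the included COVID cases at their groups". Neither Figure 2 nor Figure 3 is reproduced in the text available.
- **Statistical Analysis Plan:** the primary outcomes, including 28-day mortality and the PCR result, are compared by Kruskal-Wallis without covariates. A further step is conditional: "In case of existing differences in some baseline characteristics, logistic regression will be performed". No covariates are named.

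**The concern.** There are two contradictions in the current text. One is the allocation ratio, which alone would be a minor slip. The other is whether the study is randomised at all. The two design statements cannot both be true, and no readable text describes a random list, concealment or a rule for non-random assignment.

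The design question decides the analysis. With a random list, the unadjusted group comparison is adequate, and the non-RCT label wrongly downgrades the evidence. If drugs are given according to supply or usual practice, a difference in mortality or PCR result may reflect which patients received which drug. Eligibility runs from moderate to critical disease, so severity is an obvious route. The remark that the ratio follows real use, and the SAP's own mention of confounding, both lean towards non-random assignment, but neither states it.

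**Working it through.** **1. Ratio.** The plan's own group sizes reproduce under 1:2:2 only.

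- 1:2:2 of 265: 265/5 = 53 and 265 × 2/5 = 106, which is Table 2 exactly.
- 2:1:1 of 265: 265 × 2/4 = 132.5 and 265 × 1/4 = 66.25. Group A would need 132.5/50 = 2.65 times the stated supply.

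**2. Design.** Population says randomised and Method says non-RCT. A missing figure could show an assignment scheme, but one of these two sentences would still be wrong.

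**3. What is at stake if assignment is not random.** This is an illustration.

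*From the documents:* group sizes 53/106/106; alpha 0.05; planned difference 20 points; 120 deaths and 250 admissions a month, so 120/250 = 48% mortality (assuming the two figures describe comparable periods).

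*Assumed:* critical share 30%, 40% or 50% in B and C, and 15 points higher in A; mortality 40 or 60 points higher in critical than in other patients; no drug effect; regression triggered by a baseline P-value of 0.05 or less (inferred from the SAP's significance level).

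*Chance that the baseline test misses the imbalance.* Three-group chi-square test, 2 df, noncentrality λ = Σ nᵢ(pᵢ − p̄)² / [p̄(1 − p̄)]. In every case A lies 0.12 above the pooled share and B and C lie 0.03 below it, so the numerator is 53 × 0.12² + 212 × 0.03² = 0.954.

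| Critical share A/B/C | p̄ | λ | Power | Missed |
|---|---|---|---|---|
| 45/30/30% | 0.33 | 4.31 | 0.444 | 55.6% |
| 55/40/40% | 0.43 | 3.89 | 0.406 | 59.4% |
| 65/50/50% | 0.53 | 3.83 | 0.400 | 60.0% |

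*Are the inputs coherent?* Non-critical mortality is 0.48 − p̄ × contrast. At 40 points, non-critical/critical mortality is 34.8/74.8%, 30.8/70.8% and 26.8/66.8%. At 60 points it is 28.2/88.2%, 22.2/82.2% and 16.2/76.2%. All are possible. At 20% overall mortality some combinations are not (0.20 − 0.43 × 0.60 = −5.8%; 0.20 − 0.53 × 0.40 = −1.2%), so the results are claimed at 48% only.

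*False difference, A against B and C:* imbalance × contrast.

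- 0.15 × 0.40 = 0.06 (52.8% against 46.8%), and 0.06/0.20 = 30% of the planned difference.
- 0.15 × 0.60 = 0.09 (55.2% against 46.2%), and 0.09/0.20 = 45%.

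*Rejection by the unadjusted mortality test with no drug effect:* 0.099 and 0.167 by the same noncentral formula. Simulating Kruskal-Wallis on the binary outcome (200,000 runs per case) gives 0.098 to 0.100 and 0.166 to 0.168.

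*Only the runs in which the baseline test is not significant:* mean false difference 0.040 to 0.042 (40 points) and 0.059 to 0.063 (60 points); rejection 0.060 to 0.073.

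**4. Can an adjusted model be supported?** Expected deaths are 265 × 0.48 = 127. Two group terms and three covariates make five parameters: 127/5 = 25 deaths per parameter, or 127/6 = 21 with a fourth covariate. No PCR rate is given. Ten events per parameter with five parameters needs 50 patients with the rarer result, and 50/265 = 19% if all are tested.

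**The case against.** The strongest reply is that the SAP does plan for confounding: it provides logistic regression on the primary outcomes when baseline characteristics differ. If that regression governs whenever it is triggered, the relevant error rate is the 6% to 7% seen when the imbalance is missed, not 10% to 17%, and the residual bias is 4 to 6 points. This stands as a limit on the size. It does not remove the point, because the SAP does not say that the regression replaces the unadjusted test, names no covariates, and makes adjustment depend on what is observed.

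The miss rate also concerns a single yes/no variable and an inferred trigger. Several other day 0 measures reflect severity and could prompt adjustment, so 56% to 60% is not the chance that severity goes unadjusted. The imbalance and mortality contrasts have no source in the documents. They show what could happen, not what to expect.

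The 48% mortality relates deaths among all hospitalised patients to the current admission rate, while the trial excludes patients expected to die within 48 hours. Trial mortality may be lower, and the 127 deaths may be optimistic. At ten per parameter, however, five parameters need only 50 deaths, or 19% mortality.

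The unavailable figures may show an assignment scheme. The claim that no method is given is therefore confined to the readable text. The contradiction is not affected.

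Finally, adjustment can only address what is recorded. The Introduction reports greater benefit in seronegative patients and in those with high viral load, yet neither is listed among the baseline measurements. That limits what an adjusted analysis can claim but does not make it the wrong choice.

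**Conclusion.** The concern holds and must be fixed. The ratio in Population is wrong by the plan's own numbers, and the documents settle it as 1:2:2. The design contradiction is not settled, and it determines both the primary analysis and how far the conclusion can go. Neither finding rests on any assumption.

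The size of the possible bias does. If assignment is not random, and under the assumed 15-point imbalance and 40 to 60 point mortality contrast at 48% mortality, the unadjusted comparison is off by 6 to 9 points on average and rejects falsely in 10% to 17% of trials. Where the baseline test on that one variable misses the imbalance, the bias is still 4 to 6 points although rejection is only 6% to 7%. In those trials the main harm is a biased estimate, more than an inflated error rate. If assignment is by a random list, this bias does not arise and only the wording is at fault.

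**What to change.** 1. In Population, replace 2:1:1 by 1:2:2 (53/106/106).
2. The sponsor states how each patient is assigned, and Population and Method are reconciled to that statement.
   - **If not randomised:** remove the word randomised from Population and state the assignment rule. In the SAP, make the primary analysis of 28-day mortality, and likewise of the PCR result, a logistic regression on group, adjusted whatever the baseline P-values for covariates fixed in advance. As a minimum use age, WHO progression score and SOFA score at day 0, and consider relevant medical history. Report the unadjusted tests as secondary, and word conclusions as adjusted associations. Restate the power statement in Sample Size for the adjusted model, since it now rests on ANOVA or Kruskal-Wallis.
   - **If randomised:** remove the non-RCT label from Method and describe the 1:2:2 random list and its concealment. The unadjusted comparisons can stay primary.

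**Cost:** wording changes in two protocol sections and a statement of the assignment method. On the non-randomised branch, there is also an SAP change, a revised power statement and a more modest conclusion. The covariates named are already planned for collection at baseline, so the model needs no new data.
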